#### Safety

Safety data will be evaluated descriptively, including all recruited study patients who received at least one dose of study therapy (safety population). Results will be reported by mean parameter estimates and associated 95% confidence intervals.

#### Secondary endpoints

Statistical analysis of the pre-specified secondary endpoints will be performed with descriptive and inferential statistical methods. Secondary outcomes will be evaluated and compared between the randomized treatment arms using the following methods. In case of normally or non-normally distributed metric outcomes, Student's t test or the Mann-Whitney U test will be applied, respectively. Categorical outcomes will be analyzed using Fisher's exact test (2x2 tables) or the Chi test (>2x2 tables). Survival data will be analyzed using the Kaplan-Meier method and the log-rank test. Hazard ratios will be estimated based on Cox proportional hazards models after checking the proportional hazards assumption based on the Schoenfeld residuals.

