### 3.2.2 Secondary Endpoints

- occurrence of AKI within 72h after cardiac surgery (according to the KDIGO criteria)
- occurrence of moderate and severe AKI within 72h after cardiac surgery (according to the KDIGO stage 2 and 3)
- amount of volume application within 12h after randomization
- fluid status 12h after randomization
- dose of vasopressor use during intervention
- creatinine clearance on day one after cardiac surgery
- free-days through day 28 of vasoactive medications and mechanical ventilation
- renal recovery at day 90 (renal recovery is defined as serum creatinine levels  $< 0.5$  mg/dl higher than baseline serum creatinine (creatinine level before surgery)
- 30-day, 60-day and 90-day mortality
- length of ICU stay
- length of hospital stay
- use and duration of renal replacement therapy within hospital stay
- use of RRT at days 30, 60, 90
- MAKE90 (major adverse kidney events consisting of mortality, dialysis dependency, persistent renal dysfunction (defined as serum creatinine  $\geq 2x$  compared to baseline value) at day 90
- Effect of ACEi/ARBs use on the AT II effect
- Correlation between the severity of hyperreninemia and the AT II effect

Other variables:

- Surveillance of vital parameters on ICU
- Safety laboratory parameters
- Occurrence of thromboembolism
- Adverse events

Add-on study:

- determination of further biomarkers (e.g. KIM-1, chitinase, NGAL, renin, hyaluronic acid and anti- and pro-inflammatory cytokine levels (IL-6, IL-10...), leukocyte functions

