#### 5.2.2 Exclusion Criteria

1. Preexisting AKI (stage 1 and higher)

2. Patients with cardiac assist devices (ECMO, LVAD, RVAD, IABP)
3. Pregnant women, nursing women and women of childbearing potential
4. Known (Glomerulo-) Nephritis, interstitial nephritis or vasculitis
5. CKD with eGFR < 30 ml/min
6. Dialysis dependent CKD
7. Prior kidney transplant within the last 12 months
8. Emergency surgery in the context of an acute coronary syndrome
9. Hypersensitivity to the active substance, or to any of the excipients of the study medication
10. Bronchospasm
11. Liver failure
12. Mesenteric ischemia
13. Participation in another intervention trial in the past 3 months
14. Persons with any kind of dependency on the investigator or employed by the institution responsible or investigator
15. Persons held in an institution by legal or official order

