### 5.2.3 Distribution of Gender in the Study Population

We expect a gender distribution of (male: female) 70:30. No patient will be excluded from the study on the basis of gender. Gender will be used for covariate adjustment in the final analysis. A subgroup analysis will be performed according to gender.

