#### T1 Baseline (after registration)

- Demographic data, admission diagnosis, category of admission
- Safety laboratory test
- Concomitant medication

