### **9.5 Study Assessments**

- Blood and urine samples for Add-on-Trial

Blood and urine samples will be collected at 4h after CPB and at 0, 12, and 24h after randomization through routinely placed catheters. The samples will be centrifuged and stored immediately at -80°C until measurement of biomarkers (e.g. NGAL, KIM-1). New renal biomarkers will be assessed. For this the samples will be stored not more than 10 years.

- Safety laboratory test

- complete blood count (thrombocytes included),
- potassium-, sodium-, ionized and total calcium levels
- creatinine, creatinine-clearance, BUN and eGFR,
- pH, bicarbonate
- bilirubine,
- CRP
- PCT
- Coagulation parameter (INR, prothrombin time, thrombin time, fibrinogen, antithrombin)
- Acute kidney injury
  - AKI will be defined according to the KDIGO criteria (see 18.1.2)
- Length of hospital stay
  - Cumulative days from hospital admission until hospital discharge
- Length of ICU stay
  - Cumulative days from ICU admission until ICU discharge
- Major adverse kidney events (MAKE)
  - combined endpoint consisting of mortality, dialysis dependency, persistent renal dysfunction (defined as serum creatinine  $\geq 2x$  compared to baseline value) at day 90

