#### Multivariable statistical analyses

Multivariable statistical analyses will be applied in order to identify independent prognostic factors of clinical outcomes. The identified prognostic factors will allow determining risk groups of patients with expected outcomes of different severity. Survival data will be analyzed using multivariable Cox proportional hazards models after checking the proportional hazards assumption based on the Schoenfeld residuals. Binary outcomes will be analyzed by multivariable logistic regression. Model building will be performed using stepwise variable selection based on Akaike's information criterion (AIC) in order to identify relevant and meaningful independent variables of a respective outcome. Models will be fitted and model parameters will be estimated using Maximum Likelihood methods. The final models will be validated using cross-validation techniques.

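### Day-one creatinine clearance is tested as an unadjusted level although pre-operative kidney function is collected, which gives up precision the trial could have at no cost

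*Protocol*

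**What the plan says.** Section 3.2.2 of the protocol lists as a secondary endpoint "creatinine clearance on day one after cardiac surgery". The synopsis and Section 3.1.2 list it too, in each place as a post-operative level with no reference to a starting value.

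Section 12, under secondary endpoints, fixes the comparison for every continuous outcome: "In case of normally or non-normally distributed metric outcomes, Student's t test or the Mann-Whitney U test will be applied, respectively".

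Pre-operative kidney function is collected. Section 9.1 lists "Safety laboratory test" at the T1 baseline visit, and Section 9.2 lists it again on postoperative days 1 to 3. Section 9.5 gives the panel's content, including "creatinine, creatinine-clearance, BUN and eGFR". The flow chart (Section 1.2) names creatinine, BUN and eGFR for the same panel but not creatinine clearance.

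Nothing else in the protocol brings baseline kidney function into this comparison:
- Section 5.2.3 names one covariate: "Gender will be used for covariate adjustment in the final analysis". Section 12 contains no model that uses it.
- The multivariable part of Section 12 covers survival data by Cox models and, for the rest, "Binary outcomes will be analyzed by multivariable logistic regression". It looks for prognostic factors and has no model for continuous outcomes.
- Section 6 gives 1:1 randomisation and names no stratification factor.

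**The concern.** Day-one creatinine clearance is the only continuous kidney-function endpoint. The other kidney outcomes are already anchored to a starting value: the primary biomarker endpoint is a change from randomisation, renal recovery and MAKE90 compare creatinine with baseline, and so does KDIGO creatinine staging. This one is not.

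Eligibility has a lower limit on kidney function, "CKD with eGFR < 30 ml/min" in Section 5.2.2, and no upper limit, so patients can differ considerably before surgery. (The synopsis puts this limit at 20; the two need reconciling, but the point does not depend on which applies.) As far as those differences persist to day one, they are noise in an unadjusted comparison. With about 30 patients per arm the loss may matter, because Section 4 describes a feasibility trial whose data are to support a follow-up trial.

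**Working it through.** **Inputs from the protocol (Section 12).** 30 evaluable patients per arm, two-sided alpha 0.05. The sample size reproduces: 30/(1 − 0.05) = 31.6, so 32 per arm and 64 in total. No precision or power figure is stated for creatinine clearance.

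**Assumptions.** SD 25 ml/min at baseline and on day one; correlation ρ between the two of 0.3, 0.5 or 0.7. The protocol gives neither.

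**1. Unadjusted comparison.** SE = 25 × √(2/30) = 6.45 ml/min. With 58 degrees of freedom, t = 2.00 and the 95% half-width is 2.00 × 6.45 = 12.9 ml/min.

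**2. Adjusted comparison.** ANCOVA multiplies the residual variance by (1 − ρ²) and uses one more degree of freedom (57). Half-width = 2.00 × 6.45 × √(1 − ρ²). The equivalent sample size without adjustment is 30/(1 − ρ²) per arm. Power is from the noncentral t distribution, for a true difference of 0.515 SD (12.9 ml/min), which the unadjusted test detects with 50% power.

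| ρ | Variance removed (ρ²) | 95% half-width, ml/min | Equivalent n per arm | Power |
|---|---|---|---|---|
| unadjusted | – | 12.9 | 30 | 50% |
| 0.3 | 9% | 12.3 | 33 | 54% |
| 0.5 | 25% | 11.2 | 40 | 62% |
| 0.7 | 49% | 9.2 | 59 | 78% |

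Half-widths scale with the SD. At SD 20 the unadjusted value is 12.9 × 20/25 = 10.3, and at SD 30 it is 12.9 × 30/25 = 15.5. The other three columns do not depend on the SD. The table leaves out the effect of chance baseline differences on the adjusted SE, on average a variance factor of about 1 + 1/56, which widens the adjusted half-widths by about 0.9%.

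**3. What a chance baseline difference does.** With equal SDs, a difference b in pre-operative means shifts the unadjusted estimate by about ρb. A 5 ml/min difference shifts it by 0.5 × 5 = 2.5 or 0.7 × 5 = 3.5 ml/min, against a half-width of 12.9.

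Given b and no drug effect, the unadjusted estimate is normal with mean ρb and standard deviation 6.45 × √(1 − ρ²), and the test rejects beyond ±1.96 × 6.45:
- b = 0.25 SD (6.25 ml/min), exceeded in 33% of trials: rejection 4.9%, 4.7% and 3.6% at ρ = 0.3, 0.5 and 0.7.
- b = 0.5 SD (12.5 ml/min), exceeded in about 5% of trials: rejection 7.8%, 12.6% and 19.9%.

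**4. Over all randomisations.** Simulated type I error at ρ = 0.5 and 0.7 was 4.5% to 4.8% for the t test and Mann-Whitney test, and 5.0% for ANCOVA.

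**The case against.** A reader might infer that an imbalance in pre-operative kidney function will pass for a drug effect. The documents do not support that. Allocation is randomised, so the planned tests hold their level (step 4), and chance imbalance is already reflected in the width of the confidence interval. Under the same SD of 25, a baseline difference above 5 ml/min arises by chance in 44% of trials, which sounds alarming. But only a fraction ρ of it reaches the estimate, and even 0.25 SD (6.25 ml/min) does not lift the false-positive rate above 5% (step 3). A misleading result needs a much larger imbalance, which is uncommon.

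Four further objections have some force.
- **The gain is assumed.** Bypass surgery lies between the two values, in patients selected for high AKI risk, so the correlation could be low. At ρ = 0.3 the gain is under 5 points of power. This stands, and is why a range is shown.
- **Pre-operative clearance may not exist.** The flow chart omits it from the panel, and the protocol does not say whether clearance is measured or estimated. If it needs timed urine, 24-hour urine volume is scheduled only from the operation day. This stands, but pre-operative creatinine and eGFR appear in both places and can serve as covariate.
- **A statistical analysis plan may adjust.** It may, but the protocol itself names unadjusted tests for these outcomes, and its one planned covariate is gender.
- **It is one of many secondary endpoints in a feasibility trial.** True, and this limits the weight of the point.

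**Conclusion.** The point holds as a loss of precision on one secondary endpoint. Section 12 fixes an unadjusted comparison of day-one levels although pre-operative kidney function is available. The planned tests remain valid, and a chance imbalance enters the estimate only in proportion to the correlation, without systematic bias.

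Under the stated assumptions the gain ranges from minor at ρ = 0.3 to the equivalent of almost doubling the sample at ρ = 0.7. It rests on the assumed correlation, on similar SDs at both times, and on a pre-operative measure being recorded. It is a desirable improvement and not a flaw that endangers the trial's conclusions.

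**What to change.** Add to Section 12, or to the statistical analysis plan before unblinding:
- Analyse day-one creatinine clearance by ANCOVA with treatment arm and the pre-operative T1 value as covariate. Use pre-operative creatinine clearance if it is recorded before surgery, otherwise pre-operative eGFR or creatinine, and name the choice in advance.
- Fix the scale and its effect measure beforehand: an adjusted difference with 95% CI on the original scale, or an adjusted ratio with 95% CI on the log scale.
- Keep the t test or Mann-Whitney comparison as a sensitivity analysis.

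Prefer ANCOVA to a simple change score, which beats the unadjusted level only if the correlation exceeds 0.5. Align the flow chart with Section 9.5 on whether the panel includes creatinine clearance, and state how it is obtained.

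Cost: a few lines of text and one degree of freedom. No new data are needed, since creatinine and eGFR are already in the baseline panel.

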#### Multivariable statistical analyses

Multivariable statistical analyses will be applied in order to identify independent prognostic factors of clinical outcomes. The identified prognostic factors will allow determining risk groups of patients with expected outcomes of different severity. Survival data will be analyzed using multivariable Cox proportional hazards models after checking the proportional hazards assumption based on the Schoenfeld residuals. Binary outcomes will be analyzed by multivariable logistic regression. Model building will be performed using stepwise variable selection based on Akaike's information criterion (AIC) in order to identify relevant and meaningful independent variables of a respective outcome. Models will be fitted and model parameters will be estimated using Maximum Likelihood methods. The final models will be validated using cross-validation techniques.

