## 1.2 Flow Chart

Visit	T1 S 	T2 R  B 		T3 OD	T4-T6 POD 1-3	T7 Dis-charge /POD 7	T8 POD 30	T9 POD 60	T10 POD 90
Informed Consent	X								
Inclusion and Exclusion criteria	X								
Renin measurement before and after cardiac surgery (4 hours after cardiopulmonary bypass)			X	X					
Registration		X							
Demographic data Age, sex, BMI, comorbidities (EuroSCORE, hypertension, coronary artery disease, congestive heart failure, NYHA, peripheral vascular disease, diabetes, previous stroke or transient ischemic attack, chronic liver disease, chronic kidney disease, chronic obstructive pulmonary disease, cancer), medication (b-blockers, ACEi/ARBs, diuretics, anticoagulation)			X						
Admission diagnosis, Category of admission (elective, emergency)			X						
Surgical parameters nature of surgical procedure, duration of surgical procedure, duration of CPB, duration of aortic cross clamp				X					
Randomization				X					
Urinary [TIMP-2]*[IGFBP] measurement At randomization and 12 h after start of intervention				X					
Intervention / Study medication				X					
APACHE II				X					
Hemodynamics (MAP, HR, CVP)				X	X				
Pressors				X	X				
SOFA-Score				X	X				
KDIGO criteria					X				
Fluid balance / 24h urine volume				X	X				
Concomitant Medication N-acetylcysteine, amphotericin, aminoglycosides, cyclosporine, tacrolimus, radiocontrast agents, diuretics				X	X				
Safety laboratory test Complete blood count, potassium-, sodium-, creatinine and BUN and eGFR, pH, bicarbonate, bilirubin, CRP, PCT, coagulation parameter		X			X				
Add-on study				X 	X 				
Mortality						X	X	X	X
Length of stay (ICU, Hospital)						X		X	
Duration of ventilator support / duration of administration of vasopressors						X	X		
Number of days of RRT/RRT dependence						X			X
(Serious) adverse events				X	X	X	X	X	X

 Screening

 Registration

 Baseline ( prior operation until randomization)

 Blood and urine samples will be collected 4h after CPB, 12h and 24h after start of study medication

 Blood samples will be collected on POD 2 and 3

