#### Sample size

The expected median [TIMP-2]\*[IGFBP7] level in the control group is median control=0.84 (Q1=0.35, Q3=1.57) and in the AT-II group median AT-II=0.58 (Q1=0.26, Q3=1.20), based on Meersch et al., Intensive Care Med 2017. A total number of 64 patients will be recruited and a number of 32 patients will be randomized to each of the two treatment arms. With an expected 5% dropout rate, up to 2 patients per treatment arm will be non-evaluable. With a number of n=30 evaluable patients per treatment arm, the location shift between the distributions of the biomarker [TIMP-2]\*[IGFBP7] in the AT-II and the control group can be estimated with an expected precision  $\pm 0.285\text{ng/ml}^2/1000$  (half-width of the 90% confidence interval).

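### Stepwise AIC selection in about 60 patients is likely to yield spurious prognostic factors, and cross-validating only the selected model could appear to confirm them

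*Protocol*

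**What the plan says.** Protocol section 12, under Multivariable statistical analyses, sets the aim: "Multivariable statistical analyses will be applied in order to identify independent prognostic factors of clinical outcomes". For binary outcomes the tool is logistic regression ("Binary outcomes will be analyzed by multivariable logistic regression"); for survival outcomes it is Cox regression. Variables are chosen as follows: "Model building will be performed using stepwise variable selection based on Akaike's information criterion (AIC". Estimation is by maximum likelihood, and no shrinkage is mentioned. On validation the text says "The final models will be validated using cross-validation techniques", and on use of the result "The identified prognostic factors will allow determining risk groups of patients with expected outcomes of different severity".

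The data come from a small trial: "A total number of 64 patients will be recruited and a number of 32 patients will be randomized to each of the two treatment arms", and "With an expected 5% dropout rate, up to 2 patients per treatment arm will be non-evaluable". The paragraph lists no candidate predictors, does not limit model size relative to events, does not call the analysis exploratory, and does not say what is repeated inside the cross-validation folds.

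**The concern.** Stepwise selection by AIC is lenient. With few events and many candidates it retains variables that have no relation to the outcome, and maximum likelihood then overstates their coefficients. Cross-validation guards against this only if the selection is part of what is cross-validated. If the variables are chosen on all patients and only the coefficients are refitted in the folds, the held-out patients have already influenced the choice, and the validated performance is biased upwards.

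This differs from low power, which gives an inconclusive result. Here the output can look positive: named factors, risk groups and a reassuring AUC, all possibly from noise. Section 4 describes a feasibility trial whose data will support an application for a further trial, so spurious factors could carry forward.

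**Working it through.** **Sample size (Sample size paragraph of section 12).** 30 / (1 − 0.05) = 31.6, so 32 per arm and 64 in total. 5% of 32 is 1.6, rounded up to 2. The plan's figures reproduce: 2 × 30 = 60 evaluable.

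**Events (assumption).** Section 2.1 gives an AKI rate of up to 30% for cardiac surgery patients in general: 0.30 × 60 = 18 events. No rate is given for this renin-selected, vasopressor-treated group, so 10% (6 events) and 50% (30 events) were also tried.

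**Candidates (assumption).** The protocol fixes no number. The flow chart's baseline block begins "Age, sex, BMI, comorbidities (EuroSCORE, hypertension, coronary artery disease, congestive heart failure, NYHA" and holds 19 items: 3 demographic, 12 comorbidity and 4 drug classes. There are also 4 surgical items. I used 5, 10 and 19. With 18 events that is 18/5 = 3.6 down to 18/19 = 0.95 events per candidate.

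**Analytic check.** AIC = −2 log L + 2p, so a one-parameter term enters when it lowers −2 log L by more than 2. Under the null, P(χ²₁ > 2) = 0.157. For k independent noise candidates, the chance that at least one qualifies is 1 − (1 − 0.157)^k: 57% for k = 5, 82% for k = 10 and 96% for k = 19.

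**Simulation.** The setting was n = 60, an outcome unrelated to any candidate, and independent candidates (about one third continuous, the rest binary). Selection was forward/backward AIC logistic regression with at most 10 terms. Five-fold stratified cross-validation was done in two ways: refitting the already selected model only, or repeating the selection in each fold. A run that selected nothing counted as AUC 0.50. True performance was the AUC in 400 new patients. With 18 events and 300 runs per column:

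| | 5 candidates | 10 | 19 |
|---|---|---|---|
| At least one noise variable kept | 61% | 86% | 96% |
| Mean number kept | 0.9 | 1.9 | 3.8 |
| At least one with p < 0.05 in the final model | 22% | 43% | 75% |
| Apparent AUC | 0.60 | 0.68 | 0.76 |
| AUC, only the final model cross-validated | 0.59 | 0.65 | 0.70 |
| AUC, selection repeated in each fold | 0.50 | 0.51 | 0.50 |
| AUC in new patients | 0.50 | 0.50 | 0.50 |

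The Monte Carlo standard error of the 61% is √(0.61 × 0.39 / 300) = 2.8 percentage points. A separately programmed simulation of the same setting gave 56%, 85% and 93% for the first row and 0.57, 0.64 and 0.70 for cross-validation of the final model only. It again gave about 0.50 with selection repeated.

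**Sensitivity to events (19 candidates, 200 runs each).** Cross-validating only the final model gave AUC 0.69 with 30 events and 0.82 with 6 events. Repeating the selection gave 0.50 in both.

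**The case against.** **The validation step.** A reader might infer that the plan definitely selects on all patients and then validates with contaminated folds. The text does not establish this. Cross-validating the final models is the literal wording, but repeating the selection in each fold is not excluded, and fold design could be set in a statistical analysis plan that is not shown. This part stands, so false validation is a possibility and not a certainty. It does not rescue the rest. The protocol itself fixes stepwise AIC, unpenalised estimation and the risk-group claim, and noise variables are still selected when the cross-validation is done properly.

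**The size.** A reader might also take the 19-candidate figures as a forecast for this trial. They are not. The flow chart is a data-collection schedule and does not name model candidates; the 30% is an upper figure for a broader population; and treating every candidate as independent noise is a null calibration. Some baseline items may be truly prognostic, and correlated candidates would lower the rates somewhat. A range is therefore the fair summary. Even at 5 candidates, though, a noise variable is kept in about 60% of runs.

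**The importance.** Finding prognostic factors is not among the objectives or endpoints in section 3, and the synopsis methods do not mention it. No efficacy or safety comparison depends on it. That limits the weight of the point but does not remove it, because the risk-group sentence carries no exploratory label.

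**Conclusion.** The point holds in a bounded form. With about 60 evaluable patients, the stated selection rule is likely to produce at least one spurious prognostic factor: roughly 60% of null trials with 5 candidates and 96% with 19, at 18 events. If the validation is carried out as literally worded, it could lend those factors an AUC of about 0.58 to 0.70 when the true value is 0.50. The event count, the number of candidates and their independence are assumptions; the 0.157 threshold and the 60 patients are not.

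The unqualified claim about risk groups is more than this design can support. The consequence is confined to the prognostic-factor and risk-group statements. Nothing here affects the primary biomarker comparison.

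**What to change.** In section 12, Multivariable statistical analyses:

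1. State that the whole selection procedure is repeated within every cross-validation fold or bootstrap sample, and that the resulting optimism-corrected performance is the one reported.
2. Replace the sentence on determining risk groups with a statement that the prognostic models are exploratory and hypothesis-generating.

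The first change removes the false validation but does not stop noise variables from being selected, which is why the second is also needed. A few pre-named predictors, or a penalised model, are optional alternatives to stepwise selection.

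The cost is protocol wording (matched in any statistical analysis plan) and a little programming; no extra patients or data are required. The downside is that the reported discrimination will be less favourable.
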